### **3.2.1 Study Design Justification**

#### **Justification for two treatment groups**

Eptinezumab is the fifth treatment option made available to people living with migraine for prevention of migraine attacks. As such the decision that insurers and prescribers must make is, "What benefit does this new treatment create over those options currently available?" In particular, payers must consider whether to add eptinezumab to their formulary. Thus, whether eptinezumab improves efficacy over the basket of available treatments is the key question, rather than whether it is superior to a single treatment.

#### **Justification for 6-month observation period**

It is known that patients experience an early onset of efficacy with eptinezumab, and pooled analyses with other advanced preventives indicate that this early onset provides a comparative advantage to eptinezumab. However, less is known regarding the sustainability of this advantage. The durability of effect is a key element in the decision making of payers, thus 6 months is considered the minimum relevant period of observation.

### **Justification for an open-label study**

EVEC is intended to be a real-world evidence study to answer the question for patients, prescribers and payers seeking to know the comparative effectiveness of eptinezumab in actual clinical practice. In the real-world, patients and their professional caregivers (physicians and staff) know what medication the patient receives; therefore, the same principal applies here. In addition, masking participants to treatment assignment in this study would require that every participant receive at least two of the following: 1) monthly sham injection; 2) 30 in-office sham injections in their head and face quarterly; or 3) a quarterly sham infusion. While this may reflect an internally valid study design, it is far from a real-world clinical experience.

### **Justification for use of an active comparator/no placebo**

As noted above, this is a real-world study to evaluate the comparative effectiveness of eptinezumab against other advanced preventives for migraine. The justification for comparison to a “market basket” of current treatments is noted above in the “Justification for two treatment groups.” We note here that we consider only an active comparator and no placebo because in a real-world setting no patient would receive a placebo. So only active comparators are considered.

## **3.3 Additional Study Rationale and Considerations**

### **Study Population**

Most payers in the US, as well as AHS treatment guidelines, require failure of two generic oral preventive medications before initiating treatment with an advanced preventive. Therefore, this is the target population for this study. While many payers require failure of at least one advanced preventive therapy before initiation of eptinezumab, this is due to economic, not clinical, considerations. Therefore, a purpose of EVEC is to assist payers in understanding the economic and clinical cost, if any, to patients and society of these decisions. In addition, we are limiting the sample to people experiencing at least 8 migraine days per month as these patients (i.e., high-frequency EM and CM patients) are those most likely to be referred for advanced preventive therapy.

### **Selection of doses**

Dosing of all medications will be consistent with each product’s FDA approved label. Treating physicians and their patients might use any dosage consistent with labelling and good clinical practice.

### **Primary objective**

This is a pilot study, as such, there is no primary objective. All objectives are exploratory.

## 4 Ethics

### 4.1 Ethical Rationale

EVEC will provide patients, prescribers and payers important information regarding the comparative effectiveness of the studied treatments for migraine prevention to support decision making by these stakeholders. Information comparing the effectiveness of these treatments in a real-world setting is not currently available from any scientific source. Randomization to the various treatments included in the study is justified due to the equipoise that is created by this lack of information.

The participant will be fully informed about the study including the risks and benefit of his/her participation in the study.

The participant may withdraw from the study at any time, for any reason, specified or unspecified, and without penalty or loss of benefits to which the participant is otherwise entitled.

In accordance with *Good Clinical Practice*, qualified medical personnel at Lundbeck will be readily available to advise on study-related medical questions. Safety data will be reviewed regularly by Lundbeck's U.S. Pharmacovigilance department to ensure that prompt action is taken, if needed.

In accordance with *Good Clinical Practice*, the investigator will be responsible for all study-related medical decisions.

### 4.2 Informed Consent

No study-related procedures, including any screening procedures, may be performed before the investigator has obtained written informed consent from the participant.

Changing (for example, discontinuing or down-tapering) a participant's concomitant medications prior to the Screening Visit to ensure that the participant meets the selection criteria is a study-related activity and must not occur before the Informed Consent Form has been signed.

It is the responsibility of the investigator or person designated by the investigator to obtain written informed consent from the participant. The informed consent process may be delegated, however, the requirements for the delegates must be documented prior to the start of the study. National laws must always be adhered to when allowing potential delegation. Any delegation must be documented in the site delegation log.

The investigator must identify vulnerable participants, that is, participants whose willingness to participate in this study might be unduly influenced by the expectation, regardless of whether it is justified, of benefits associated with participation, or of a retaliatory response

from senior members of a hierarchy in case of refusal to participate. Participants thus identified must be excluded from participation in the study.

Prior to obtaining written informed consent, the investigator or a designee must explain to the participants the aims and methods of the study and any reasonably expected benefits and foreseeable risks or inconveniences to the patients.

The participants must be informed:

- that their participation in the study is voluntary and that they are free to withdraw from\ the study at any time without justifying their decision
- of their right to request a copy of their personal data from the study via the investigator
- of the possibility of withdrawing consent (see section 8.9) of their right to receive information about the study results from the investigator on the patients' own initiative; the results will be available approximately 1 year after the end of the study

The participants must be informed that persons authorized by Lundbeck and authorized personnel from certain authorities (domestic, foreign, data protection agencies, or institutional review boards [IRBs]) may view their medical records. The participants must also be informed that de-personalized copies of parts of their medical records may be requested by authorized personnel from certain authorities (domestic, foreign, data protection agencies, or IRBs) for verification of study procedures and/or data. The confidentiality of the patients will in all cases be respected. The participants must be given ample time and opportunity to enquire about details of the study prior to deciding whether to participate in the study.

It is the responsibility of the investigator to ensure that all questions about the study are answered to the satisfaction of the participants. Prior to allowing a participant to participate in the study, an Informed Consent Form must be signed and dated by the participant and signed and dated by the investigator or a designee on the same day. The participants must be given a copy of the signed *Informed Consent Form*.

#### **4.3 Personal Data Protection**

The data collected in this study will be processed in accordance with the specifications outlined in the Danish Data Protection Act and the European Union legislation to ensure that requirements regarding personal data protection are met. If an external organization will process data on behalf of Lundbeck, a contractual procedure will be signed between Lundbeck or delegate and the external organization to ensure compliance with the above--mentioned legislation.

#### **4.4 Institutional Review Board**

This study will be conducted only after Lundbeck has received confirmation that the regulatory authorities have approved or confirmed notification of the study and that written approval of the protocol has been granted by the appropriate IRB.

The investigator must not allow any participants to participate in the study before receiving confirmation from Lundbeck or the CRO that the required approvals and/or notifications have been received. Permission for an investigator to start enrollment will be provided to the investigator in writing from Lundbeck or the CRO.

The IRB must be informed when specific types of protocol amendments have been made and written approval must be obtained before implementation of each amendment, if required by local law.

If applicable, interim reports on the study and reviews of its progress will be submitted to the IRB by the investigator at intervals stipulated in its guidelines.

## **5 Study Population**

### **5.1 Number of Participants**

Two hundred participants are planned for enrollment into the trial.

Adult participants with at least 8 or more migraine days per month, in two of the last three months prior to enrollment, who are being seen at participating sites and who meet the other inclusion and exclusion criteria will be invited to participate in the study.

The informed consent will include an explanation of the following:

1. Prior to randomization, participants will complete a decision exercise using a decision guide created to inform participants on treatment options for migraine prevention. Then participants will complete the SDM-Q-9 to indicate what they think would be their preferred migraine prevention treatment (see [Appendix IV](#)), followed by completion of the SURE Test (see [Appendix VI](#)).
2. The consent form will inform the patient that the treatment preference indicated after the review of the decision guide will not impact the treatment to which they are randomized. Additionally, the consent form will clearly indicate that should the patient not agree to initiate treatment with the medication to which they were randomized, their participation in the study will be discontinued.
3. Regardless of the treatment the participant is randomized to, the cost of the study medication (i.e., eptinezumab, Botox, erenumab, fremanezumab or galcanezumab) and administration will be covered by Lundbeck for the six-month duration of the trial.

### **5.2 Participant Recruitment**

Participants will be competitively recruited from approximately 10 sites in the US that offer all therapeutic options in the study.

The investigators will be notified immediately when the recruitment period comes to an end.

### 5.3 Selection Criteria

Participant selection is based on the inclusion and exclusion criteria listed below.

Participants who meet each of the inclusion criteria and none of the exclusion criteria at the Screening Visit and prior to first medication dose at Baseline (Visit 2) are eligible to participate in this study.

#### **Inclusion Criteria**

1. The participant is able to read and understand the Informed Consent Form.
2. The participant has signed the Informed Consent Form.
3. The participant is aged  $\geq 18$  years of age.
4. Have a diagnosis of migraine per IHS ICHD-3 guidelines at least 12 months prior to screening.
5. Have a history of  $\geq 8$  migraine days/month in two of the previous three months as confirmed by the treating physician through medical records.
6. Have a history of failure of at least 2 previous oral migraine preventive treatments as defined in the AHS Consensus Statement (see [Appendix II](#)).
7. Be able to understand the clinical description of treatment options and have the capability to participate fully in making their treatment preferences known.
8. Be willing to accept randomization to any of the possible study medications if allocated to that treatment arm.
9. Have no restriction in venous access that would restrict the ability to receive infusion treatment.
10. Be willing and capable of completing daily reports and other participant reported outcome measures using a smartphone-based application.
11. Have their own smartphone or tablet and agree to allow the study application to be downloaded to it.
12. Agree to not post any personal medical data or information related to the study on any website or social media site (e.g., Facebook, Twitter) during the study.
13. Be able to read, understand and complete all required forms and questionnaires in English.

#### **Exclusion Criteria**

1. The participant has previously been enrolled in this study.
2. The participant is a member of the study personnel or of their immediate families or is a subordinate (or immediate family member of a subordinate), to any of the study personnel.
3. The participant has a history of severe drug allergy or hypersensitivity, or known hypersensitivity or intolerance to either eptinezumab, erenumab, fremenezumab, galcanezumab or their excipients.
4. The participant has previous history of use of any of the study drugs (i.e. eptinezumab, Botox, erenumab, fremenezumab or galcanezumab). Participants who have used oral

CGRP inhibitors atogepant or rimegepant for prevention are also excluded. Note that only previous Botox use for treatment of migraine is exclusionary. Prior use of Botox for cosmetic purposes is allowed. Participants with a history of acute use of rimegepant or ubrogepant (but not for prevention) are permitted to enroll.

5. The participant has a diagnosis of CM and has hypersensitivity to botulinum toxin preparation or to any of the components in the formulation.
6. The participant has used opioids or butalbital-containing products greater than 4 days per month in the last month.
7. The participant is pregnant, <6 months post-partum, or breastfeeding.
8. The participant has a disease or takes medication that could, in the investigator's opinion, interfere with the assessments of safety, tolerability, or efficacy, or interfere with the conduct or interpretation of the study.
9. The participant is, in the investigator's opinion, unlikely to comply with the protocol or is unsuitable for any reason.

#### **5.4 Participants with Medication Overuse Headache**

Participants with a dual diagnosis of CM along with medication overuse headache (MOH) attributable to regular acute medication overuse (e.g. triptans, ergotamine, or combination analgesics greater than 10 days per month) are eligible for enrollment in the study.

Participants with CM and MOH who use opioids or butalbital-containing products greater than 4 days per month will be excluded. The participant's clinician will determine if participants meet the criteria for MOH. The ICHD-3 criteria (listed below) and MOH checklist (see [Appendix XVII](#)) will be provided to the clinical sites for them to make their assessments. The participant's MOH status will be noted in the CRF.

ICHD-3 criteria for MOH:

- Headache occurring on  $\geq 15$  days/month in a participant with a pre-existing headache disorder
- Regular overuse for  $> 3$  months of one or more drugs that can be taken for acute and/or symptomatic treatment of headache
- Not better accounted for by another ICHD-3 diagnosis.

#### **5.5 Withdrawal Criteria**

Information on participants who withdraw from the study will be collected in the withdrawal section of the CRF.

A participant must be withdrawn from the study if:

- the participant withdraws their consent (defined as a participant who explicitly takes back their consent); section [8.9](#) states how the patient's data will be handled
- the participant is lost to follow-up (defined as a participant who fails to comply with scheduled study visits or contact, who has not actively withdrawn from the study, and

for whom no alternative contact information is available [this implies that at least two documented attempts have been made to contact the patient])

- the investigator considers it, for safety and/or study compliance reasons, in the best interests of the participant that they be withdrawn from treatment
- All participants will be permitted to withdraw at their choice or upon advice of their treating physician. Information collected from the participant prior to withdrawal will remain in the study data set.

No participant will be withdrawn from the study due to non-compliance with treatment. As this is a pragmatic real-world study, the failure to comply with treatment is considered a real-world outcome. However, an investigator may withdraw a participant from the study based upon their medical judgement if they deem continued involvement in the study is detrimental to the participant's welfare.

Products purchased with study-specific vouchers cannot be used for an off-label indication. Participants must meet the criteria for CM at baseline in order to be randomized to onabotulinumtoxinA (Botox®). Participants who do not comply with this requirement will be withdrawn from the study.

Participants who become pregnant will be withdrawn from the study and counselled to enroll in the Lundbeck pregnancy registry. The Lundbeck pregnancy registry is a prospective, observational study in the United States that will be initiated prior to the end of this trial.

Participants who withdraw will not be replaced.

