**Panel 3: Post-Baseline eDiary Collected Assessments**

Assessments	Reporting Schedule				
	Daily	Weekly (a)	Monthly (b)	Quarterly (c)	Early Termination
Daily Headache Status Report: - Did they have a headache in the previous 24 hours? Y/N	X				X
If answer is “Yes” to “Daily Headache Status” then participants will be prompted to report their Daily Headache Symptoms: - What symptoms did they experience with the headache? - How do they rate the severity of the symptoms? - What was the most “bothersome” of the symptoms (i.e. PI-MBS)?	X				X
If answer is “Yes” to “Daily Headache Status” then participants will be prompted to report their Acute Headache Medication Usage: - What medication(s) did they take (if any) to relieve the headache? - How do they rate the effectiveness of the medication(s) taken?	X				X
If answer is “Yes” to “Daily Headache Status” then participants will be asked if they considered this headache to be a migraine.	X				X
If answer is “No” to “Daily Headache Status” then participants will be prompted to respond to the following: - Do they have any residual symptoms lingering between headaches? - Have they experienced any “warning” symptoms prior to a headache? - What degree of impact did each of these symptoms have?	X				X

Assessments	Reporting Schedule				
	Daily	Weekly (a)	Monthly (b)	Quarterly (c)	Early Termination
Healthcare Resource Utilization	X (d)				X
EQ-5D-5L		X			X
Good Day/Bad Day Scale		X			X
PSS			X		X
HIT-6			X		X
PAM-10				X	X
MIDAS				X	X
SDM-Q-9				X	X
TSQM				X (e)	X

(a) Weekly = every 7 days, Visit 2 date = Day 0 (b) Monthly = every 28 days, Visit 2 date = Day 0

(c) Quarterly = every 84 days, Visit 2 date = Day 0 (d) Will be assessed 3 times per week

(e) Assessed at Day 168 only

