### **8.9 Withdrawal Visit**

Participants who withdraw from the study prior to Visit 8 will be asked to complete an Early Termination Visit, if at all possible. The visit must be scheduled as soon as possible after withdrawal. All information collected at an Early Termination Visit is to be recorded in the Visit 8 forms of the eCRF.

In addition, all assessments normally scheduled to be completed by the participants at Visit 8 in the eDiary ([Panel 3](#)) will be completed on the day of the Early Termination Visit. In order for the PROs to be provided to the participant via the smartphone application on the day of the Early Termination Visit, site study staff will need to complete the End of Treatment form within the EDC system and select the reason for early termination. The completion of this form will notify the CRO to send the Early Termination PROs to the participant and discontinue any future notifications for PRO completion.

No new information will be collected from participants who withdraw from the study, except information collected in relation to the scheduled Withdrawal Visit or needed for the follow-up of adverse events (section 10.5).

The reason for withdrawal must be recorded in the eCRF.

For a participant who withdraws consent:

- if the participant withdraws consent during a visit and then agrees to it being the final visit, the investigator will complete the visit as a Withdrawal Visit and all the data collected up to and including that visit will be used
- if the participant withdraws consent during a telephone conversation, the investigator will ask the participant if they will attend a Withdrawal Visit. If the participant:
  - agrees to attend a Withdrawal Visit, all the data collected up to and including that visit will be used
  - refuses to attend an Early Termination Visit, the investigator should attempt to follow the participant's safety and future treatment; any information collected will only be recorded in the patient's medical records

If the participant explicitly requests that their data collected from the time of withdrawal of consent onwards not be used, this will be respected.

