3.3 Definition of Withdrawal

Withdrawal from the study is defined as termination of consent on or before Visit 8. Participants who withdraw from the study prior to Visit 8 will be asked to complete an Early Termination Visit. The visit must be scheduled as soon as possible after withdrawal. All information collected at an Early Termination Visit is to be recorded in the Visit 8 forms of the electronic case report form (eCRF). If the patient denies completing the Early Termination Visit, then no further data will be collected.

No participant will be withdrawn from the study due to non-compliance with treatment. As this is a pragmatic real-world study, the failure to comply with treatment is considered a real-world outcome. However, an investigator may withdraw a participant from the study based upon their medical judgement if they deem continued involvement in the study is detrimental to the participant's welfare.

No new information will be collected from participants who withdraw from the study, except information collected in relation to the scheduled Withdrawal Visit or needed for the follow-up of adverse events.

The reason for withdrawal must be recorded in the eCRF.

For a participant who withdraws consent:

- If the participant withdraws consent during a visit and then agrees to it being the final visit, the investigator will complete the visit as a Withdrawal Visit and all the data collected up to and including that visit will be used
- If the participant withdraws consent during a telephone conversation, the investigator will ask the participant if they might attend a Withdrawal Visit. If the participant:
 - Agrees to attend a Withdrawal Visit, all the data collected up to and including that visit will be used
 - Refuses to attend an Early Termination Visit, the investigator should attempt to follow the participant's safety and future treatment; any information collected will only be recorded in the patient's medical records

If the participant explicitly requests that their data collected from the time of withdrawal of consent onwards not be used, this will be respected.

The end of the study for an individual participant is defined as the last protocol-specified contact with that patient. The overall end of the study is defined as the last protocol-specified contact with the last patient ongoing in the study.

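### Protocol 5.5 turns an investigator's decision to stop treatment into a mandatory study exit, so outcomes that could still be reported after a safety-led stop are lost to the treatment-policy analysis

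*Protocol*

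**What the plan says.** Protocol 5.5 opens a list of events for which study withdrawal is mandatory. The third is "the investigator considers it, for safety and/or study compliance reasons, in the best interests of the participant that they be withdrawn from treatment". The list is loosely drafted, because its next item is only permissive: "All participants will be permitted to withdraw at their choice or upon advice of their treating physician". The paragraph after it states "No participant will be withdrawn from the study due to non-compliance with treatment". It then adds a discretionary rule, repeated in SAP 3.3, that "an investigator may withdraw a participant from the study based upon their medical judgement if they deem continued involvement in the study is detrimental".

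Protocol 8.9 sets the consequence of study withdrawal: "No new information will be collected from participants who withdraw from the study, except information collected in relation to the scheduled Withdrawal Visit", with adverse-event follow-up as the other exception. Completing the End of Treatment form tells the CRO to "send the Early Termination PROs to the participant and discontinue any future notifications for PRO completion".

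SAP 3.3 defines the event more narrowly: "Withdrawal from the study is defined as termination of consent on or before Visit 8". SAP 11.2.1 names two separate intercurrent events. One is stopping the index preventive, whether or not a new one is started. The other is study withdrawal, including for an adverse event or at the physician's request. SAP 11.2.3 applies treatment policy to both, using available endpoint data for the first and imputation for the second.

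**The concern.** A treatment-policy comparison needs outcomes after the drug is stopped. The third bullet of Protocol 5.5 merges stopping treatment with leaving the study. Where a site follows it, a participant taken off treatment for safety stops reporting, although the app is on their own device and most remaining visits are by telephone or video. The later weeks then rest on the MMRM, or on the within-arm missing-at-random imputation of SAP 11.2.6. That section also mentions exploring ways to penalise missing values, without specifying them.

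A participant stopped for safety may well do worse than the model predicts from others in the same arm, so the loss may be informative. It may also differ by arm. Eptinezumab and Botox have one later dosing decision, at week 12, while the monthly SC drugs have five later doses, from week 4 (Protocol 6.2). Much of the loss falls in weeks 13-24, the period Protocol 3.2.1 relies on for durability of effect.

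**Working it through.** The plan gives no figure on this point. The check is a reading of the text, a count of scheduled reports, and an illustration of size.

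**1. Does any text override the bullet for a safety-led stop?**
- The sentence on non-compliance (5.5) protects poor compliers with treatment. It does not cover an investigator's safety stop.
- The discretionary sentence (5.5, SAP 3.3) concerns harm from being in the study. It does not say that participants off treatment stay in.
- Protocol 6.1 and 6.3.1 keep permitted switchers, not participants who stop without one.
- Protocol 9.1.2 requires daily eDiary entry up to End of Treatment or Early Termination, so an early exit ends it.
- SAP 3.4 analyses everyone as randomized, but collects nothing.
- Protocol 14 allows no waivers, which leaves a site little room to soften a mandatory rule.

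The bullet therefore stands for a safety-led stop without a permitted switch.

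**2. Reports still due after a stop.** Panel 3 gives the schedule ("Weekly = every 7 days, Visit 2 date = Day 0"), with HIT-6 every 28 days and MIDAS every 84, to Day 168. The week of the stop is assumed.

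| Stop | Weekly reports due (of 24) | Of these, in weeks 1-12 | HIT-6 (of 6) | MIDAS (of 2) |
|---|---|---|---|---|
| Week 4 | 20 | 8 | 5 | 2 |
| Week 8 | 16 | 4 | 4 | 2 |
| Week 12 | 12 | 0 | 3 | 1 |

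The Early Termination set, if completed, stands in for one report of each kind that is still due.

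**3. Illustrative bias in good days per week.** All inputs are assumed except 100 per arm (SAP 15.1).
- Bias = difference between arms in the proportion stopped × gap between true and modelled good days per week × share of the window lost.
- SE = SD × √(2/100). With SD 2 this is 0.283; with SD 1.5, 0.212; with SD 2.5, 0.354.

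Upper inputs: a 5-point difference in stops, a gap of 2 days, and one Early Termination report subtracted from the weeks lost.
- Stop at week 8, weeks 1-12: 0.05 × 2 × 3/12 = 0.025, or 0.09 SE (0.12 with SD 1.5, 0.07 with SD 2.5).
- Stop at week 8, weeks 1-24: 0.05 × 2 × 15/24 = 0.0625, or 0.22 SE (0.29 and 0.18).
- Stop at week 4, weeks 1-12: 0.05 × 2 × 7/12 = 0.058, or 0.21 SE.
- Stop at week 4, weeks 1-24: 0.05 × 2 × 19/24 = 0.079, or 0.28 SE.
- Stop at week 12: nothing lost in weeks 1-12. For weeks 1-24, 0.05 × 2 × 11/24 = 0.046, or 0.16 SE.

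Lower inputs: a 1-point difference, a gap of 1 day and a stop at week 12 give 0.01 × 1 × 11/24 = 0.005 for weeks 1-24, or 0.02 SE.

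If the Early Termination set is not completed, the week-8 upper figures become 0.05 × 2 × 4/12 = 0.033 (0.12 SE) and 0.05 × 2 × 16/24 = 0.067 (0.24 SE).

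**The case against.** The strongest reply is that the bullet is a drafting slip. The rest of 5.5, the as-randomized rule in SAP 3.4 and the separate listing of discontinuation in SAP 11.2.1 all point to participants staying in the study after they stop the drug. That may well be the intent. However, no sentence says so for a safety-led stop, and the bullet is mandatory. If it is a slip, correcting it is easier still.

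Second, the SAP is not blind to such exits. It names withdrawal for adverse events and at the physician's request, and plans imputation. This stands: there is no gap in the list of intercurrent events. What remains is that imputed values replace outcomes that could have been observed.

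Third, the dosing schedule shrinks the group. Eptinezumab and Botox have no scheduled dose after week 12, so there is little left to withdraw from. Participants on those drugs may move to an SC drug at week 12, SC participants may change to another SC drug, and other prescribed preventives are unrestricted. This also stands. For eptinezumab and Botox, the week-12 row is often the relevant one.

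A reader might infer that everyone who stops the drug is lost. The documents do not support that: poor compliers with treatment and permitted switchers remain. A reader might also cap the group with the loss to follow-up of under 10% that SAP 15.1 cites from PROMISE. That does not work either, because Protocol 5.5 and SAP 11.2.1 list loss to follow-up apart from safety-led exits.

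**Conclusion.** The conflict is real but narrow. It affects participants taken off treatment for safety without a permitted switch, at sites that apply the bullet as written. Their number is not given and is probably small. Under the assumed inputs the bias is a fraction of one standard error: about 0.09 SE for weeks 1-12 and 0.22 SE for weeks 1-24 at the upper week-8 setting, and 0.21 and 0.28 SE for a stop at week 4. The 5-point difference between arms drives these figures, and nothing in the documents fixes it.

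A reader might conclude that the treatment-policy comparison is invalid. The documents do not support that. Protocol 3.3 describes a pilot with no primary objective, so no confirmatory conclusion is at stake, and missing values do have a planned analysis. The case for change is that the loss is avoidable, possibly informative and cheap to prevent. This is an optional improvement.

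**What to change.** Move the third bullet of Protocol 5.5 out of the study-withdrawal list. Record the event as treatment discontinuation, with date and reason, and continue eDiary and PRO collection to Day 168. Collection would end earlier only if:
- consent is withdrawn;
- the participant is lost to follow-up;
- another exit in 5.5 or 6.3.1 applies, such as pregnancy or a switch outside the rules; or
- the investigator judges continued study participation itself detrimental.

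Align SAP 3.3, whose definition covers termination of consent only, with the resulting list. Clarifying the reference to study compliance in the bullet is optional and would recover little. The investigator still decides when treatment stops.

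The cost is a protocol wording amendment with the IRB handling described in Protocol 4.4, one matching SAP line, and some continued site contact with participants off treatment. The data come through the app they already have.
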